months a (4-5mL) blood sample will be taken from the infant by venipuncture as well as a nasopharyngeal and rectal swab and (4-5mL) sample of breast milk from the mother. Recruitment will be from the maternity ward at the Faji Kunda health centre, and restricted to healthy singleton infants, birth weight >2.5kg, without congenital abnormalities. Informed consent will be obtained from mothers. 100 pregnant women and their newborn infants will be recruited over 6-months (allowing for a dropout rate of up to 20%).

1 Background information and rationale

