6.2 Participant's premature termination

A study participant will be discontinued from participation in the study if:

- Intercurrent illness, or other medical condition or situation occurs such that continued participation in the study would not be in the best interest of the subject.
- Development of any exclusion criteria.

Subjects are free to withdraw from participating in the study at any time without giving a reason.

[figure not shown]
This withdrawal will not affect their standard medical care.

7 Statistical considerations

Sample Size:

Assume negatively correlated skewed distributions for maternal antibody and maternal (or infant) GBS load, with Figure 2 showing a typical simulated bi-variate distribution (note scale factor not modelled – correlation is unaffected). A sample size of 150 gives 90% power to detect a correlation of -0.45 as significantly different from zero at the 1% level (adjusted down to allow for serotype multiplicity).

Figure 2 Bi-variate distribution of antibody and bacterial load.

With the absence of further variability parameters it is not possible to conduct a classical sample size calculation. Although the study is powered on measuring correlation (i.e. linear trend), the analysis plan focuses on measuring the actual trend rather than relying on linear assumptions.

Analysis Plan

Initial analyses will be based on standard summary statistics comparing maternal and infant responses. Graphical methods with spline smoothers will be used to examine trends and if appropriate (linear trends), correlations will be used to summarize the relationships. Cross-tabulations will compare means (with 95% confidence intervals), medians (with inter quartile ranges), with histograms to compare distributions.

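### The only power statement is for 150, but the protocol enrols 100 mother-infant pairs with up to 20% dropout, so power for the planned size is not stated

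*Protocol*

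**What the plan says.** The protocol summary gives the number of participants as 100. Its description of the study design repeats the figure and attaches the dropout allowance to it: "100 pregnant women and their newborn infants will be recruited over 6-months (allowing for a dropout rate of up to 20" percent).

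Section 7 (Statistical considerations, Sample Size) uses a different number. It assumes negatively correlated, skewed distributions for maternal antibody and for maternal or infant bacterial load, refers to a simulated bivariate distribution, and states: "A sample size of 150 gives 90% power to detect a correlation of -0.45 as significantly different from zero at the 1% level". The level is explained as "at the 1% level (adjusted down to allow for serotype multiplicity"; five serotypes are named in section 2.1, and 5%/5 = 1%. The same section says that a classical calculation is not possible because variability parameters are lacking, and that the study is powered on measuring correlation.

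No part of the protocol states power for 100 or 80 pairs, or says where 150 comes from.

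**The concern.** Section 7 is the only justification of the study's size, and it refers to 1.5 times the planned enrolment (150/100) and almost 1.9 times the smallest number expected at the last visit (150/80 = 1.875). Anyone approving the study, or later reading a null result for one serotype, would take 90% power for a correlation of -0.45 to stand behind the 100 pairs. The protocol gives no basis for that.

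Both numbers stand in the protocol itself, so this is not a detail that can be left to a separate analysis plan.

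**Working it through.** **Inputs**
- Planned enrolment: 100 pairs (protocol summary).
- Dropout: up to 20% (protocol summary).
- Size in the power statement: 150; power 90%; correlation -0.45; level 1% (section 7).
- Sidedness: not stated. Two-sided is assumed, from "as significantly different from zero".
- Parameters of the skewed simulation: not given in the text of section 7.

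**Step 1. Can 100 and 150 be reconciled?**
- 100 recruited less 20% leaves 100 × 0.8 = 80.
- If 100 were the evaluable number, recruitment would be 100/0.8 = 125, still below 150.
- If 150 were the number recruited, 150 × 0.8 = 120 would remain, which is not 100.
- Counting mothers and infants separately gives 200, and a correlation uses pairs.
- Pooling visits does not give 150 either. Section 7 repeats the analyses separately at each time point, and section 3.1 takes the maternal swab only in labour.

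None of these readings connects the two figures.

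**Step 2. The printed figure by the ordinary formula.** Fisher z: power = Φ(atanh|r| × √(N − 3) − z), with atanh(0.45) = 0.4847 and z = 2.576 (two-sided 1%).
- N = 150: 0.4847 × √147 − 2.576 = 3.30, power 99.95% (one-sided 99.98%).
- By the same formula, 90% power needs N = ((2.576 + 1.282)/0.4847)² + 3 = 66.3, so 67 (one-sided: 59).

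The printed 90% does not reproduce this way. Rank-correlation variance factors (1.06, or 1 + r²/2) do not bring it down to 90% either: they give 99.9% at 150.

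**Step 3. Could a skewed model give 90% at 150?** Section 7 gives no parameters, so those used here are assumptions: a latent normal correlation of -0.45, a Pearson test at two-sided 1%, and 1,500 replicates.

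| Assumed margins | N = 150 | N = 100 | N = 80 |
|---|---|---|---|
| Exponential | 99% | 90% | 78% |
| Lognormal, log-SD 0.75 | 97% | 82% | 70% |
| Lognormal, log-SD 1.0 | 75% | 47% | 30% |

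A value of 90% at 150 lies between the two lognormal cases, so strong skewness could produce it. The result depends on which correlation is set to -0.45. With log-SD 0.75 and -0.45 imposed on the raw scale instead, power is 99.7% or more at all three sizes. The printed figure is therefore unverifiable from the text, but not shown to be wrong.

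**Step 4. Power at the planned size for r = -0.45, under each reading**

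(a) Printed 90% at 150 taken at face value. The implied effect per √(N − 3) is (2.576 + 1.282)/√147 = 0.318, equivalent to inflating the Fisher z variance by about 2.32.
- N = 100: Φ(0.318 × √97 − 2.576) = Φ(0.558) = 71%.
- N = 80: Φ(0.318 × √77 − 2.576) = Φ(0.216) = 59%.

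(b) Ordinary Fisher z, two-sided 1%.
- N = 100: Φ(0.4847 × √97 − 2.576) = Φ(2.198) = 98.6%.
- N = 80: Φ(0.4847 × √77 − 2.576) = Φ(1.677) = 95.3%.

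Readings (a) and (b) are different models and must not be combined. Under (b), N = 150 would have 99.95% power, not 90%.

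**The case against.** The strongest reply is that the mismatch is one of documentation. With the protocol's own correlation and level, the standard formula gives more than 90% power even at 80 pairs. The study is a non-interventional cohort, its first objective is descriptive, and section 7 says the analysis will focus on the actual shape of the trend. All of this stands. A reader might infer from the gap between 150 and 100 that the study is underpowered; the protocol does not support that. The fall to 71% or 59% follows only if the printed 90% at 150 is accepted as the output of a simulation whose parameters are not given.

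It is also fair that 80 should not be applied everywhere. Cord blood and the first swabs are taken at or near birth, and final enrolment follows the birth and the eligibility check (section 4.1). Later dropout therefore does not reduce the birth analyses, which can use up to 100 pairs. The 80 is the worst case for the last visit.

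The reply does not remove the inconsistency. The standard formula cannot rescue the printed figure, because it disagrees with that figure at 150, and section 7 itself says a classical calculation is not possible. Whichever model was meant, the power for 100 or 80 pairs is not in the protocol.

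**Conclusion.** The inconsistency stands: enrolment is 100 pairs, the only power statement is for 150, and no reading of the dropout allowance connects them. The printed 90% does not apply to the planned study.

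For a correlation of -0.45 at the two-sided 1% level, power at the planned size is either about 71% (100 pairs) and 59% (80 pairs), if the printed 90% at 150 is taken at face value, or 98.6% and 95.3% under ordinary Fisher z. The first pair assumes that the required size scales as in Fisher z with a constant variance inflation; the second assumes bivariate normal data, which section 7 does not. A reader might also infer that the 90% at 150 is an error. It does not reproduce from the stated inputs by the standard formula, but a strongly skewed model could produce it. The supportable conclusion is that sensitivity at the planned size is unstated and cannot be worked out from the protocol.

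**What to change.** In section 7, replace 150 with the planned numbers: up to 100 pairs for the birth analyses and, with 20% dropout, 80 at the last visit. Rerun the skewed-distribution simulation at N = 100 and N = 80. Print either the power for a correlation of -0.45 or the correlation detectable with 90% power. Beside it, state the distributions and parameters used, the scale on which the correlation is defined, and whether the test is one- or two-sided. If a Fisher z figure is also given, label it a normal-theory approximation, so that it is not read as the result of the skewed model.

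The cost is a short rerun and a few lines in a protocol amendment. Enrolment, visits and sampling do not change. The sponsor should accept that the restated power may be less favourable than the printed 90%.

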2.1 Study endpoints

1. Serotype-specific GBS colonisation in mothers and infants

Prevalence of serotype-specific GBS carriage in mothers and their infants and changes in infant carriage over time will be determined by culturing rectovaginal swabs and infant nasopharyngeal and rectal swabs in selective microbiological media for GBS.

2. Serotype-specific GBS antibody concentration

Serotype-specific GBS antibody-concentration (Ia, Ib, II, III, V) in blood and breast milk will be determined at each of the three time points using flow cytometry.

3. GBS-antibody function

Serotype-specific GBS antibody function (Ia, Ib, II, III, V) will be determined in blood and breast milk using complement C3b/C5 deposition and flow cytometric methods.

3 Study design

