5.2.2 Laboratory evaluations

Swab culture

Rectovaginal swabs will be taken from all mothers at presentation in labour and sent same day to the MRC laboratory. Nasopharyngeal and rectal swabs will be taken from all infants and sent same day to the MRC laboratory. Maternal and infant swabs will be pre-cultured overnight in Todd Hewitt Broth and cultured by plating on selective blood agar plates for 48 hours. If there is any bacterial growth this will be identified as GBS by latex agglutination test and serotyping by RT-PCR.

Cord blood and at 2 to 3-months of age

Additional experiments will be done from the cord blood samples and from the infants at 3-months of age in order to complete the antibody aspect of this study. The blood samples will need to be transported to MRC laboratories in EDTA tubes within 6 hours of collection, spun down and frozen at -70 degrees. The samples will be batched and sent to Porton Down, UK for serotype-specific antibody analysis and complement deposition studies.

Breast milk

Additional experiments will be done from breast milk samples collected at birth, day 6 and day 60. Women will be asked to hand express 1-2mL of colostrum at the first visit and 4-5mL of breast milk on day 6 and day 60. Breast milk should be expressed from each breast and collected in two sterile universal containers. The samples need to go immediately into cold storage and transferred same day to the laboratory. The samples then need to be aliquoted into 100uL samples and frozen at -70 degrees. Batches of breast milk will then be sent to Porton Down for antibody analysis and complement deposition studies.

Sample handling Cord blood and 3 months

Spin sample, take off serum into two aliquots and PLACE SAMPLE STRAIGHT IN -70°C & RECORD LOCATION IN WORKSHEETS

Table 2 - Laboratory experiments

Experiment	Time course	Volume required	Method	Sample storage
1. Microbiological swab culture	48 hours (12-56 hours)	1 combined rectovaginal swab (mother) 1 nasopharyngeal swab, 1 rectal swab (infant)	See SOP	Store at 4 degrees until culture. Culture at 37 degrees
2. Antibody surface labeling studies	4 hrs (3.5- 4.5 hrs)	>2mL	See SOP	Serum in YELLOW tubes, spin down and aliquot into 2 aliquots and store at -70°C

3. Complement deposition studies	4 hrs (3.5- 4.5 hrs)	>2mL	See SOP	Serum in YELLOW tubes, spin
· ·	4.5 hrs)			
studies				down and
				aliquot into 2
				aliquots and
				store at -70°C

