Formal analysis will be based on linear regression for each serotype and will test whether maternal antibodies predict colonization in newborns. Antibody responses will be suitably transformed to satisfy the normality and constant variance assumptions for the regression based analyses. As the relationships are likely to be non-linear fractional polynomials will be used to model non-linearity. In addition to analyses based on continuous data, responses will be categorized and contrasts used to make appropriate comparisons. Where possible regression will be adjusted for potential confounders including mothers with high levels of carriage who have not yet mounted an antibody response, infants without antibody and maternal and infant infections. With both maternal and infant longitudinal sampling, separate analyses will be repeated at each time point. Discrete analyses

based on carriage will be analyzed using a survival analysis approach. With multiple time points and multiple serotypes from the same subjects, false discovery rates will be used to control for false positives from multiple hypothesis tests.

8 Data handling and record keeping

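### Carriage is described as present or absent, but the power basis assumes a bacterial load and the formal model is linear regression

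*Protocol*

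**What the plan says.** **Endpoint (Protocol 2.1).** The first endpoint is carriage prevalence: "Prevalence of serotype-specific GBS carriage in mothers and their infants and changes in infant carriage over time will be determined by culturing" the swabs.

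**Laboratory (Protocol 5.2.2, Swab culture).** "Maternal and infant swabs will be pre-cultured overnight in Todd Hewitt Broth and cultured by plating on selective blood agar plates for 48 hours". Then: "If there is any bacterial growth this will be identified as GBS by latex agglutination test and serotyping by RT-PCR". No colony count or other quantification is described for any swab.

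**Sample size (Protocol 7).** "Assume negatively correlated skewed distributions for maternal antibody and maternal (or infant) GBS load". The 90% power at N=150 refers to a correlation of -0.45 between these two quantities.

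**Analysis plan (Protocol 7).** The formal analysis is "Formal analysis will be based on linear regression for each serotype and will test whether maternal antibodies predict colonization in newborns". Next comes "Antibody responses will be suitably transformed to satisfy the normality and constant variance assumptions for the regression based analyses". The plan adds fractional polynomials, categorised responses with contrasts, and adjustment for mothers with high carriage levels. It also says "separate analyses will be repeated at each time point", and that discrete analyses "based on carriage will be analyzed using a survival analysis approach".

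**The concern.** Linear regression with normal, constant-variance errors suits a continuous outcome. Colonisation as the laboratory section describes it is a 0/1 result per serotype and visit. Transforming antibody does not help when antibody is the predictor, because the normality and variance assumptions concern the errors of the outcome. Fractional polynomials change the shape of the trend but leave the outcome on the probability scale with constant variance.

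Objective 2 is at stake. A surrogate marker needs the risk of colonisation at a given antibody level, with a trustworthy interval. A test of no association is not enough for that. A power statement about load also says little about what the study can show for a sparse yes/no outcome.

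**Working it through.** **1. The plan's own figure.** Fisher's z gives power = Φ(atanh(0.45)·√(n−3) − z). With n=150 and two-sided 1%: 0.4847 × 12.124 − 2.576 = 3.30, so power is 99.95%, not 90%. About 67 pairs would give 90%. The simulated distribution behind the plan's figure is not shown, so its method cannot be checked exactly. The figure concerns load, so it does not settle this point either way.

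**2. Expected colonised infants at birth.** Inputs are 100 recruited, or 80 after 20% dropout (Protocol summary), maternal carriage of 22-24%, and transmission of 15-50% (Protocol 1.1).

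- Of 100: 100 × 0.22 × 0.15 = 3.3, to 100 × 0.24 × 0.50 = 12.0
- Of 80: 80 × 0.22 × 0.15 = 2.6, to 80 × 0.24 × 0.50 = 9.6
- Per serotype, if split evenly over five (assumption): 0.7 to 2.4 of 100
- In one dominant serotype holding half (assumption): 3.3/2 = 1.65 to 12/2 = 6 of 100

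**3. Linear regression on a 0/1 outcome at these prevalences.** Each scenario had 8,000 simulated studies with n=100 and a standardised normal antibody value. Coverage is that of the nominal 95% ordinary least-squares interval for the best linear slope, among runs with at least one event. The odds ratios are assumptions; the protocol gives none.

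| Prevalence | OR per SD | Coverage | Coverage, robust (HC3) | Mean share of fitted risks below 0 |
|---|---|---|---|---|
| 12% | 0.5 | 0.929 | 0.932 | 0.057 |
| 12% | 0.25 | 0.900 | 0.941 | 0.157 |
| 3.3% | 0.5 | 0.903 | 0.851 | 0.097 |
| 3.3% | 0.25 | 0.800 | 0.877 | 0.191 |
| 2% | 0.5 | 0.921 | 0.831 | 0.111 |
| 2% | 0.25 | 0.852 | 0.868 | 0.198 |

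With n=80, the same six cells covered 0.830 to 0.932. With no association, coverage was 0.946-0.952 at every prevalence from 2% to 24% (n=100), and the rejection rate was 0.048-0.054 in the runs from 2% to 12%. At 24% prevalence with an association, coverage was 0.954-0.956. At 2% prevalence, about 13% of studies of 100 had no event and gave no estimate (0.98^100 = 0.13).

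One run with a skewed antibody value (12%, odds ratio 0.5) over-covered, at 0.992. The direction of the error therefore depends on the predictor's distribution. The table applies when the planned transformation succeeds.

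**4. Survival analysis and birth carriage.** In simulated data with 78 of 133 events at birth, a Cox slope was -0.421 (SE 0.084) with time-zero events kept. It was identical with all times shifted by one day, and -0.340 (SE 0.133) only when the birth events were dropped.

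**The case against.** **Load may be measured.** The analysis plan speaks of carriage levels, the timeline in the appendix lists real-time PCR beside culture, and full procedures are left to SOPs that are not shown. This stands in part. A reader might infer that no load is recorded, but the documents support only that no quantification is described. Section 5.2.2 names PCR only for serotyping growth, and overnight enrichment makes a usable load unlikely.

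**Antibody may be the response.** Transforming antibody to normality would then make sense, and the plan treats discrete carriage analyses separately. The wording is ambiguous, but the sentence naming the formal analysis has antibody predicting colonisation. The reverse regression would not give risk by antibody level.

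**The simulation is not the full plan.** It fits a straight line, whereas the plan allows fractional polynomials and categorised contrasts. That is fair for the negative fitted risks, which belong to a straight-line fit. It does not change the outcome scale.

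**Sparse events are as much to blame as the linear link.** This stands: robust errors still covered only 0.83-0.88 at 2-3.3% prevalence. The remedy must therefore address sparsity too.

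**Birth events.** A reader might infer that the survival analysis discards infants positive at birth. The protocol names no survival model, time origin or rule that does so. It also repeats analyses at each time point, which keeps birth carriage, and a Cox fit can retain time zero. Such detail may lie in the SAP.

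**Conclusion.** The protocol is inconsistent on the outcome scale. The described read-out is presence or absence by serotype, the power basis is a continuous load, and the formal model is linear. At the prevalences implied by its own rates, nominal 95% slope intervals cover about 80-93% if antibody protects, and up to about 20% of straight-line fitted risks are negative. This rests on assumed odds ratios of 0.25-0.5 per SD, a roughly normal transformed antibody, and at least one event.

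It would go too far to say that the intervals are invalid in general. Coverage is near nominal with no association or at 24% prevalence, and the test of no association keeps about 5% error. The defect lies in estimating risk by antibody level. The documents do not support a claim that birth carriage is lost.

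**What to change.** - **Analysis plan, carriage at each visit.** Replace linear regression with Firth-penalised (or exact) logistic regression of carriage on log antibody. Pool across serotypes where events per serotype are too few. Report odds ratios and predicted risk by antibody level. Fractional polynomials can stay, on the log-odds scale.
- **Carriage over the three swabs (clarification).** Name a repeated-measures logistic model, or a discrete-time or interval-censored model, that counts carriage at birth as an event. Section 3.1 dates the third infant swab both at day 48 and at day 56-90; these passages must be reconciled before visit intervals are defined.
- **Sample size.** Restate the power basis for binary carriage. If load is measured, describe how it is quantified and keep the continuous model for that outcome.

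**Cost.** The binary route needs a protocol or SAP amendment and standard software, with no new data. With 3 to 12 events per 100 infants, intervals will be wide under any method, and the present power statement will no longer apply. Coverage of the penalised model was not simulated here and should be checked at the expected event counts before the plan is fixed.

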1.1 Background information and rationale

GBS Epidemiology

In resource-rich countries GBS is the most common cause of serious bacterial infections in the first week of life (early onset, EO) and of meningitis in the first 3 months of life (late onset, LO), with long-term adverse neurodevelopmental outcomes in up to 30%(1,2). Limited data from three African countries reveal a significant burden of disease (1.21-2.06/1000 live births) including meningitis (4,5,6).

GBS-acquisition occurs through vertical transmission in 15%-50% of infants born to a vaginally/rectally-colonized mother (a prerequisite for EO and risk factor for LO disease)(7,8,9). EOGBS disease can be prevented by intrapartum antibiotics (IAP) and, in a number of resource-rich countries; EOGBS is significantly less common following the introduction of IAP strategies (10,11). However, IAP protection is incomplete and has no impact on LOGBS. In resource-poor countries IAP use poses additional logistical and financial problems and is poorly implemented (12). Maternal vaccination has the greatest potential for preventing invasive neonatal GBS-disease globally.

Although GBS-colonisation is common, few colonized infants subsequently develop invasive disease (estimated 1-2%)(13,14). Despite relatively high maternal carriage rates (22-23%)(15), 13-year old reports have previously shown low invasive GBS-disease rates in the Gambia (16). Possible explanations are: the prevalence of less virulent strains; differing GBS-serotypes, USA/European invasive GBS-serotypes are predominantly serotype-III (17-20) whilst Gambian GBS-serotype studies report serotype-V predominance(21). The difference in invasive disease prevalence could also be due to higher levels of transplacentally-acquired protective antibody; Suara et al. (1998) reported high mean maternal serotype-III antibody levels in women colonised with any GBS-serotype that might account for the rarity of GBS-disease in The Gambia and other resource-poor countries (21). Alternatively, the role of GBS might have been underestimated because of

inadequate culture techniques and microbiological methods (22). In the past six months we have confirmed the predominance of serotype V antibody in pregnant Gambian women and established GBS-invasive disease prevalence of 1.2/1000 live births in a small hospital-based cohort (unpublished data).

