3.1 Type of study and design

Study design

Study Design (See Figure 3 for study design).

This is a prospective cohort study, based at Faji Kunda Health Centre of pregnant women recruited at 37 weeks gestation from the antenatal clinic at Faji Kunda and their infants from birth to 3 months of life.

Interventions

- a. Samples in labour: combined rectovaginal swabs will be taken from mothers in labour and nasopharyngeal and rectal swabs their infants at birth. 1mL of colostrum taken within 72 hours of birth, 4-5 mL of cord blood.
- b. Samples at day 6: nasopharyngeal and rectal swabs from infants, 1-2 mL breast milk
- c. Samples at day 56-90: nasopharyngeal and rectal swabs from infants, 4-5 mL breast milk, 2-3mL infant serum

Data Collection

A case report form (CRF) will capture information on:

Epidemiological data:

a) maternal: Site of delivery, mode of delivery, antenatal risk factors for infection (Premature rupture of membranes/chorioamnionitis/maternal fever/raised white cell count), number of live births, information on maternal vaccination status, information of any infections leading up to delivery requiring antibiotics, time in hours of rupture of membranes prior to delivery.

b) infant: gestational age, birth weight, stillbirths/neonatal deaths/perinatal complications

(birth asphyxia/meconium staining/signs of severe infection in the first three months of life (fever >38.5 degrees, raised white cell count, meningism). Gestational age calculated by last menstrual period or midwife palpation or ultrasonography if available.

Sample Collection

- 1) Maternal/infant carriage:
 - a) Maternal swabs: Combined-vaginal-rectal swabs in labor from all mothers who have been consented in the antenatal clinic.
 - b) Infant swabs: nasopharyngeal and rectal swabs in the first 24 hours after birth of all infants whose mothers have been enrolled into the study, second infant swabs on day 6 and final infant swabs collected at day 48

[figure not shown]
2) Antibody Carriage Serum:

[figure not shown]
a) Maternal serum: Cord blood or maternal serum sample at delivery to determine antibody levels.

b) Infant serum: at two months using venipuncture.

3) Antibody Carriage Breast milk:

Breast milk will be collected at day 0, 6 days and 2-3 months post-partum. The women will be given non-sterile surgical gloves and asked to manually express several drops of milk, which were discarded before collecting the specimen directly into the test tube.

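### The regression of newborn colonisation on maternal antibody does not condition on maternal carriage of the same serotype, and the one carriage item it lists can make the bias worse

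*Protocol*

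**What the plan says.** Protocol section 7 (Analysis Plan) sets a separate linear regression per serotype, which "will test whether maternal antibodies predict colonization in newborns". It names no restriction to infants of colonised mothers. Adjustment is to be made where possible, and the confounders given as included are "mothers with high levels of carriage who have not yet mounted an antibody response" and "infants without antibody and maternal and infant infections". Maternal carriage of the serotype under test is not among them.

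Section 3.1 provides for "nasopharyngeal and rectal swabs in the first 24 hours after birth of all infants whose mothers have been enrolled into the study", whether or not the mother is colonised. The same section has every consented mother swabbed in labour, and section 5.2.2 has GBS isolates serotyped. The conditioning variable is therefore already collected.

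Section 1.1 describes vertical transmission to 15%-50% of "infants born to a vaginally/rectally-colonized mother" and gives maternal carriage as 22-23% in earlier reports and 24% in current unpublished data. It also cites a report of "high mean maternal serotype-III antibody levels in women colonised with any GBS-serotype" and suggests, from infant data, that colonisation may contribute to antibody development.

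**The concern.** Carriage of a serotype exposes the infant to it and may also raise the mother's antibody to it. The section 7 item about mothers who have not yet responded presumes that carriage induces antibody. If so, a regression over all infants mixes two things: carriers' infants are the ones who become colonised, and carriers are the ones with more antibody. A real reduction in transmission can then look weaker, absent or reversed.

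Objective 2 in section 2 seeks an antibody marker that could stand in for protection in vaccine trials. A null or positive slope produced in this way could be read as evidence against that marker.

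**Working it through.** The protocol gives no figure for this association, so there is none to reproduce. The check asks what the all-infant regression returns when the truth is known.

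**Inputs from the protocol (section 1.1):** maternal carriage 22-24%; transmission 15%-50%.

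**Assumed:**
- same-serotype carriage of 5% (about one fifth of 24%), with 24% as the upper end;
- transmission of 30% at the carriers' mean antibody, inside the 15%-50% range;
- true odds ratio of 0.50 per SD among infants of carriers;
- log antibody with SD 1, higher in carriers by δ = 0, 0.5 or 1 SD;
- no acquisition except from a carrying mother.

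**Model:** C ~ Bernoulli(carriage); A = δC + N(0,1). Y = 0 if C = 0; otherwise logit P(Y=1) = a + ln(0.50)·A. There were 2,000,000 pairs per setting. The low-antibody-carrier column adds an indicator for carriers whose antibody is below the non-carrier mean, which is one reading of the protocol's item.

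| Carriage | δ | All infants, OR per SD | Adding low-antibody-carrier indicator | Infants of carriers only |
|---|---|---|---|---|
| 5% | 0 | 0.64 | 1.25 | 0.50 |
| 5% | 0.5 | 1.05 | 1.82 | 0.50 |
| 5% | 1 | 1.66 | 2.37 | 0.50 |
| 24% | 0 | 0.62 | 1.18 | 0.50 |
| 24% | 0.5 | 0.94 | 1.60 | 0.50 |
| 24% | 1 | 1.35 | 1.87 | 0.50 |

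Repeat runs differ in the second decimal; rounded over runs, the all-infant ranges are about 0.62-0.65, 0.95-1.03 and 1.35-1.65.

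**Hand check at 5%.** Under this model the odds of carriage rise by exp(δ) per SD of antibody. For a rare outcome, the all-infant OR is roughly the no-rise value times exp(δ): 0.64 × 1.65 = 1.06 at δ = 0.5, and 0.64 × 2.72 = 1.74 at δ = 1. Both are close to the table. The sign turns near δ = ln(1/0.64) = 0.45.

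**Wider range.** With transmission at 15% or 50%, carriage from 4.8% to 24%, and 0% or 0.2% acquisition by infants of non-carriers, the all-infant OR is 0.55-0.75 (no rise), 0.84-1.17 (0.5 SD) and 1.19-1.88 (1 SD). Adjusting for same-serotype carriage gives 0.51-0.61, and restricting to carriers gives 0.50-0.51.

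**Linear slope, as section 7 literally specifies.** At 24% carriage, 50% transmission and 0.2% background acquisition, the unadjusted slope is -0.0375, 0.008 and 0.0452 for δ = 0, 0.5 and 1. Adjusted for carriage it stays between -0.0373 and -0.0376.

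**Why the listed item hurts.** It absorbs the low-antibody carriers, whose infants are most often colonised. What remains is largely high-antibody carriers against unexposed infants, which pushes the slope upwards.

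**Information available.** Carriers of any GBS: 100 × 24% = 24, down to 80 × 22% = 17.6 with 20% dropout. With assumed serotype shares of 20-40%, one serotype has about 4-10 carriers. At 5% carriage and 30% transmission, 100 dyads give 100 × 0.05 × 0.30 = 1.5 colonised infants per serotype. The binomial chance of at most one is 56%, or 66% with 80 dyads.

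**The case against.** The strongest objection is that carriage may be partly a mediator. The sample size section begins "Assume negatively correlated skewed distributions for maternal antibody and maternal (or infant) GBS load", which allows antibody to lower maternal carriage. With the same set-up, let antibody lower carriage at an assumed OR of 0.50 per SD and have no effect on transmission. The all-infant OR is then 0.52 (5% carriage) or 0.59 (24%), while the carriers-only OR is 1.0. Restriction alone would discard a real association, and objective 2 speaks of the relationship between antibody and neonatal carriage in general. This stands: the all-infant analysis should be kept.

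A reader might infer that the protocol documents a large antibody rise in carriers. It does not. The cited maternal report concerns serotype III in women carrying any serotype, with no non-carrier figure, and the other evidence is from infants between 24 and 56 weeks and is tentatively worded. With no rise the estimate is diluted, neither hidden nor reversed.

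A reader might also infer that infants of non-carriers say nothing about transmission. That needs a perfectly sensitive labour swab and no other source of acquisition, and the protocol establishes neither. Nor does it give a carriage rate for any single serotype.

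Finally, the confounder list is open, no analysis set is defined, and an SAP might add carriage. This lowers the severity but does not dispose of the point: the protocol itself sets the test and names a carriage item in a form that can mislead.

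**Conclusion.** The point holds as a gap in the planned adjustment that should be closed before analysis. As written, the regression cannot separate antibody that blocks transmission from antibody that marks carriage, and the listed carriage item can move the estimate further from the truth (1.2-2.4 against 0.50, under the coding used here).

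How far the all-infant result departs from 0.50 depends on a rise in carriers' antibody that the documents do not give. It ranges from dilution with no rise, through near-null at about 0.5 SD, to reversal at 1 SD.

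It would go too far to say that the study will wrongly reject antibody as a correlate, or that the formal analysis should be confined to infants of carriers. The first rests on an undocumented rise. The second would remove any effect of antibody on maternal carriage and, serotype by serotype, could not be estimated from so few events.

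**What to change.** In section 7, replace the item on high-carriage mothers without antibody with maternal carriage of the same serotype at delivery, and pre-specify two analyses.

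- **(a) All infants.** Report this as the total relationship between antibody and newborn colonisation, including any effect of antibody on maternal carriage.
- **(b) Carriage-conditional.** Use serotype-matched mother-infant pairs (antibody, maternal carriage and infant colonisation all for one serotype), pooled over serotypes with clustering by mother. At birth and day 6, use infants of same-serotype carriers. At the last visit, keep all infants with same-serotype maternal carriage as a covariate.

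Single-serotype results should be descriptive. Antibody should be interpreted as a correlate of reduced transmission only from (b).

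The change is one of wording: no further sample, visit or participant is needed. The cost is precision. Analysis (b) at birth and day 6 rests on about 18-24 carrier dyads over all serotypes, and fewer if some isolates fall outside the five serotypes assayed (section 2.1). At 15%-50% transmission, 18-24 dyads yield about 3-12 colonised infants, so intervals will be wide. Pooling also assumes a similar antibody effect across serotypes, which these numbers cannot test well.
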